#### *Withdrawal criteria*

- Treatment-related toxicity.
- Voluntary withdrawal from study by participant.
- Any other intercurrent medical condition or circumstance that precludes completion of the study.

**Clinical, demographic and laboratory variables:** Data collected during each study visit will include medical history, age, gender, weight, height, RA duration, DAS28, Stanford Health Assessment Questionnaire, current medications and lifestyle assessment (diet and exercise). Type and dose of medications and the following laboratory data will be collected during each assessment visit (baseline, 1 and 6 months): renal function, erythrocyte sedimentation rate, and C-reactive protein. Adverse events and adverse drug reactions will also be recorded.

**Blood pressure and arterial function:** BP, AIx (arterial wave reflection) and PWV (arterial stiffness) will be assessed at baseline, 1 and 6 months. Clinic BP will be measured in the

morning (between 9.00am and 11.00am) in a quiet, appropriate environment at room temperature, according to current guidelines, using an automated BP monitor (UA-767PC, A&D Medical) clinically validated against the British Hypertension Society protocols. Prior to BP measurement, patients will abstain from alcohol for  $\geq 12$ -hrs, and from tobacco and caffeine for  $\geq 4$ -hrs. Patients will also be required to fast for  $\geq 6$ -hrs. The arm used for BP measurement will be free of constricting clothing to avoid impediment of the cuff. The cuff will be wrapped snugly around the upper arm with the centre of the cuff bladder positioned over the brachial artery and the lower border of the cuff approximately 2 cm above the elbow bend. The cuff will be placed at heart level by supporting the arm. Patients will sit (with legs not crossed) and relax for at least 5 min, and then three BP measurements will be taken at 2-min intervals. The average of the last two BP measurements will be calculated and used in the analyses.

Central and 24-hr BP will be assessed using PWA (SphygmoCor, AtCor Medical, West Ryde, NSW) and Mobil-O-Graph technology (I.E.M., Stolberg, Germany) available within our group. Prior to PWA, patients will abstain from alcohol for  $\geq 12$ -hrs, and from tobacco and caffeine for  $\geq 4$ -hrs. Patients will be required to fast for  $\geq 6$ -hrs. A small probe will be placed on the radial artery, and AIx and central BP measurements will take approximately 10 min. The Mobil-O-Graph will provide a 24-h assessment of peripheral and central BP, and PWV. \

**MTX-polyglutamates PGs (MTX-PGs) and 5-MTHF:** RBCs MTX-PGs concentrations will be measured at each assessment visit with a validated LC-MS/MS assay developed at the School of Pharmacy and Medical Sciences, University of South Australia. Whole blood samples will be centrifuged, plasma removed and cells are washed two times with PBS. Packed cells are then stored at  $-80$  °C prior to analysis. Stable isotope internal standard is added to 0.25mL packed RBC and proteins are precipitated with perchloric acid. MTX-PGs are purified by solid phase extraction (Strata-X Strong Cation Exchange) prior to LC separation via HILIC LC (ZIC-HILIC Column, Merck Millipore) and analysis on a Shimadzu 8060 triple quadrupole MS/MS. This assay quantifies the five MTX-PGs commonly seen in RA patients and has a limit of detection of  $<0.2$  nmol/L packed RBCs. Whole blood and plasma 5-MHTF will be measured at each assessment visit according to a method previously published. 50 $\mu$ L of whole blood or plasma is diluted with 50 $\mu$ L of 5% ascorbic acid solution containing 10mM mercaptoethanol and 10 $\mu$ L of internal standard (stable isotope labelled 5-MHTF) and incubated at 37 °C for 60 min. 60 $\mu$ L of 10% trichloroacetic acid is added, the mixture vortexed and the clear supernatant removed. 5-MHTF is separated via reverse phased LC using a Waters Acuity BEH C18 column (100X2.1mm), and detected with a Shimadzu 8060 Triple Quadrupole MS/MS.

**Genetic polymorphisms:** Pharmacogenetic variability will focus on single-nucleotide polymorphisms (SNPs) shown to be important in the effect of MTX in RA, or demonstrating a theoretical association with the cardiovascular effects of MTX: ABCB1 3435C>T (rs1045642), ABCC2 1249G>A (rs2272397), ABCG2 421C>A (rs2231142), AMPD1 34C>T (rs17602729), ATIC 347C>G (rs2372536), MTHFR 677C>T (rs1801133), MTHFR 1298 A>C (rs1801131), MTR 2756 A>G (rs1805087), MTRR 66A>G (rs1801394), SHMT 1420C>T (rs1979277), SLC19A1 80G>A (rs1051266), GGH 354G>T (rs719235) and GGH 16T>C (rs1800909). DNA will be extracted from whole blood samples and SNPs will be determined via validated Taqman™ SNP genotyping assays, performed according to manufacturer instructions. In addition, the number of 28 base-pair repeats in the promoter region of thymidylate synthase will be determined by PCR.

Adenosine: Plasma adenosine concentrations will be measured using our Waters Aquity UPLC coupled with quadrupole-time-of-flight (qToF) mass spectrometer in MS-MS mode (CIA and AI [name]), according to a method previously reported. Samples that are chilled and plasma rapidly removed from RBCs following centrifugation are stable when stored at -80 °C, through 3 freeze thaw cycles, and stored at room temperature up to 24-hr. Consequently, a protocol for rapid separation of plasma from whole blood will be adopted. To achieve the required selectivity adenosine will be extracted from plasma through protein precipitation with trichloroacetic acid followed by solid phase extraction on a Varian SPEC SCX cartridge. Furthermore, chromatographic separation on a UPLC column (Gemini NX C18, 100 x 2 mm, 3 µm) prior to MS-MS analysis will enhance assay selectivity. Isolation of adenosine from the biological matrix by SPE and UPLC removes interferences that reduce signal through ion suppression and minimises the non-specific background noise. This results in a high sensitivity assay with the ability to discriminate small, yet potentially meaningful changes in adenosine concentrations.

Asymmetric dimethylarginine (ADMA): eNOS activity will be indirectly assessed by measuring plasma ADMA, an endogenous eNOS inhibitor, at baseline, 1 and 6 months. ADMA will be measured using a validated LC-MS method on our Waters Aquity UPLC and qToF Premier mass spectrometer. Stable isotope internal standard is added to 50 µL of patient plasma followed by protein precipitation with acidified solvent. After centrifugation the supernatant layer is decanted and evaporated to dryness under vacuum. The residue is redissolved in mobile phase then analysed by reverse phase chromatography as previously published by CIA.

### **Statistical methods**

Statistical analysis will be performed using linear mixed models. In addition to providing estimated treatment effects, this analysis will also provide estimates of the individual variability in the longitudinal changes in BP and arterial function in each of the 4 groups over time. Due to the partly observational nature of the study (group 4), models will also adjust for known potential confounders, including age, gender, co-morbidities, RA duration, 5-MTHF, drugs potentially affecting BP and their doses, DAS28, biochemical parameters and inflammatory markers. Models with and without adjustment for BP will also be assessed to test the direct and indirect effects of MTX on markers of arterial function. Similarly, we will also use mediation analysis to assess the potential direct and indirect effects of MTX-PGs, adenosine concentrations and genetic polymorphisms on the associations between MTX, BP and markers of arterial function. We will perform these analyses using Mplus software (StatModel version 7.4), which provides appropriate bootstrapping routines for estimating the non-parametric 95% CIs of indirect effects.

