## **Study Title**

**Methotrexate, blood pressure and arterial function in patients with rheumatoid arthritis**

**NCT number: TBA**

**Date of the document: March 10, 2017**

## Study protocol

### Four groups of patients will be studied:

1. Newly diagnosed RA patients started on subcutaneous MTX and studied at baseline, 1 and 6 months (n=31). Patients will be initially prescribed 10 mg subcutaneous MTX once a week. Then, the dose will be adjusted based on the response by 5 mg increments up to 25 mg a week. If required, use of steroids, NSAIDs, and/or other DMARDs is allowed during the study period.
2. Newly diagnosed RA patients started on another DMARD (sulfasalazine) and studied at baseline, 1 and 6 months (n=31). Patients will be initially prescribed 500 mg sulfasalazine daily. Then, the daily dose will be increased by 500 mg each week to a maximum of 2 g daily after 4 weeks. According to clinical response, the maintenance dose will be 2-3 g daily. If required, use of steroids, NSAIDs, and/or other DMARDs (except MTX), is allowed during the study period.
3. RA patients on chronic treatment (>1 year) with oral MTX (with or without issues with tolerability, e.g. gastrointestinal side effects) at baseline and switched to subcutaneous MTX at the same dose (studied at baseline, 1 and 6 months, n=31).
4. RA patients on chronic treatment (>1 year) with other synthetic DMARDs at baseline and continued on the same DMARDs, and their dose, at 1 and 6 months (studied at baseline, 1 and 6 months, n=31).

Groups 1 and 2: randomization to subcutaneous MTX vs. sulfasalazine will be open to both patients and rheumatologists, facilitating monitoring of response and potential side effects. However, they will be asked not to disclose their treatment to the research team.

Groups 3 and 4: this is an open observational study where group 3 patients switch their oral MTX to subcutaneous MTX, and group 4 patients continue their treatment with the same DMARDs throughout the study duration.

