Study population and eligibility criteria: Adult RA patients, diagnosed according to established criteria (2010 ACR/EULAR), will be recruited from rheumatology clinics at Flinders Medical Centre (Southern Adelaide Local Health Network). Demographic and clinical characteristics and genetic polymorphisms will be assessed at baseline in newly diagnosed RA patients commencing either subcutaneous MTX (group 1) or sulfasalazine (group 2), and in RA patients already on long-term (>1 year) treatment with either oral MTX (group 3) or other synthetic DMARDs (group 4). Group 1 and group 2 (newly diagnosed RA patients) will be randomized to either subcutaneous MTX (group 1) or sulfasalazine (group 2, age- and sex-matched) in a 1:1 ratio.

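### The confounder adjustment is neither limited to baseline values nor kept off the randomised group 1 vs group 2 contrast, so visit-level covariates could change what that contrast estimates

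*Combined protocol and SAP*

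**What the plan says.** The analysis uses linear mixed models. "In addition to providing estimated treatment effects", these are to describe how individuals vary over time in each of the four groups. The adjustment sentence then opens "Due to the partly observational nature of the study (group 4" and continues that "models will also adjust for known potential confounders, including age, gender, co-morbidities, RA duration, 5-MTHF, drugs potentially affecting BP and their doses, DAS28", ending with biochemistry and inflammation markers. Its subject is the models in general. It names neither a covariate time point nor a primary model for any contrast.

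Pathways are separated for other variables only. For arterial function, "Models with and without adjustment for BP will also be assessed". Beyond that, "we will also use mediation analysis to assess the potential direct and indirect effects of MTX-PGs, adenosine concentrations and genetic polymorphisms".

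Elsewhere in the protocol:
- Study population and eligibility criteria: newly diagnosed patients "will be randomized to either subcutaneous MTX (group 1) or sulfasalazine", and "Demographic and clinical characteristics and genetic polymorphisms will be assessed at baseline".
- Clinical, demographic and laboratory variables: DAS28, type and dose of medication, renal function, ESR and CRP are recorded at baseline, 1 and 6 months.
- The MTX-polyglutamates and 5-MTHF paragraph: 5-MTHF is measured at each assessment visit.
- Description of the four groups: steroids, NSAIDs and other DMARDs may be used during the study in groups 1 and 2, except that group 2 may not add MTX. Groups 3 and 4 are together described as observational.

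**The concern.** A variable measured after randomisation may be a consequence of treatment. Disease activity, ESR and CRP follow the disease being treated, and steroids or NSAIDs may be added according to how the patient is doing. The co-medication allowed also differs by arm. Holding such a variable fixed at its visit value removes whatever part of the treatment effect runs through it. It can also add bias where the covariate and the outcome share an unmeasured cause.

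Entering current values is an ordinary way to follow the adjustment sentence in a longitudinal mixed model. The group 1 vs 2 estimate would then be a partly direct effect without a label, not the total effect of the randomised treatment. The sections on BP adjustment and mediation do not cover DAS28, ESR/CRP, 5-MTHF or concomitant drugs. Two analyses with different targets are therefore permitted for the only randomised comparison, and neither is named as primary.

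**Working it through.** **Text.** No figure in the plan bears on this point; the only documented number used below is 31 patients per group. Of the listed covariates, age and gender cannot be affected by treatment, and RA duration advances equally in both arms. DAS28, drugs and doses, renal function, ESR, CRP and 5-MTHF are all remeasured at 1 and 6 months. Nothing in the documents says which measurement enters the model, and nothing confines the adjustment to groups 3 and 4.

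**Algebra.** Let b be the slope of outcome on the visit-level covariate (outcome SD per covariate SD) and d the arm difference in that covariate. Then

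adjusted estimate = total effect − b × d.

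If d = 0 there is no shift. The direction follows the sign of b × d.

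**Precision.** With outcome–baseline correlation r (assumed 0.6, range 0.4 to 0.8):

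SE = √(2/31) × √(1 − r²) = 0.254 × 0.917, 0.800 and 0.600 = 0.233, 0.203 and 0.152 SD for r = 0.4, 0.6 and 0.8.

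With k = shift/SE, the chance that a 95% interval covers the total effect is Φ(1.96 − k) − Φ(−1.96 − k). Values of b and d are assumed, as is a systolic BP SD of 12 mmHg.

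| b | size of d (SD) | shift (SD) | mmHg | k at r = 0.6 | coverage, r = 0.6 | coverage, r = 0.4 and 0.8 |
|---|---|---|---|---|---|---|
| 0.1 | 0.25 | 0.025 | 0.3 | 0.12 | 94.8% | 95%, 95% |
| 0.2 | 0.5 | 0.10 | 1.2 | 0.49 | 92% | 93%, 90% |
| 0.3 | 0.5 | 0.15 | 1.8 | 0.74 | 89% | 90%, 83% |
| 0.4 (extreme) | 1 | 0.40 | 4.8 | 1.97 | 50% | 60%, 25% |

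**Check in a longitudinal model.** A simulation used 2,000 trials per scenario, 31 per arm, visits at baseline, 1 and 6 months, and unstructured covariance. Assumed inputs were a total month-6 effect of −0.50 SD, outcome correlation 0.6, covariate correlation 0.5, and a month-1 arm difference half that at month 6. The plan does not say how the baseline outcome is handled, so two forms were fitted: A with it as a covariate, B with it as a response visit with a common mean. Baseline covariates gave means of −0.49 to −0.51 and coverage of 93.8% to 96.0% in every scenario. Visit-level covariates gave:

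| b, d | form A (coverage) | form B (coverage) |
|---|---|---|
| 0.1, −0.25 | −0.48 (95.0%) | −0.47 (94.8%) |
| 0.2, −0.5 | −0.42 (93.0%) | −0.40 (90.8%) |
| 0.3, −0.5 | −0.38 (90.4%) | −0.35 (86.5%) |
| 0.3, +0.5 | −0.62 (91.6%) | −0.65 (88.8%) |
| 0.4, −1 | −0.18 (67.8%) | −0.11 (48.6%) |
| 0.2 or 0.3, 0 | −0.50 to −0.51 | −0.50 to −0.51 |

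Form B shows the full b × d shift; form A shows about 80% of it.

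**Unmeasured common cause.** A second illustration used 4,000 trials per setting and one follow-up visit. It assumed a total effect of −5 mmHg, a residual SD of 8 mmHg, and treatment lowering the covariate by 1 unit. Baseline adjustment stayed near −5.0 throughout. With 0, 25, 50 and 75% of the effect passing through the covariate, visit-level adjustment gave −5.0, −3.8, −2.5 and −1.3. With an unmeasured cause shared by covariate and outcome, it gave −2.9, −1.7, −0.4 and +0.8.

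**The case against.** The strongest reply is that the baseline reading is open and harmless. The plan calls its list confounders, which for a treatment comparison are ordinarily pre-treatment variables, and it places clinical characteristics at baseline. The sentence gives the observational part as its reason. Its word "also" may mean that adjusted models supplement basic ones that supply the treatment effects. All of this stands as a possible reading, but none of it is a specification. Doses of concomitant drugs and 5-MTHF fit visit-level use equally well, "also" can just as easily add a feature to the same models, and the stated reason names group 4 while the protocol treats both groups 3 and 4 as observational.

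It is also fair that the illustrations largely return their inputs. Every input except 31 per arm is assumed, and the 50% coverage in the extreme row ranges from 25% to 60% over the assumed correlations and is 67.8% under form A.

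Three stronger inferences are not supported:
- **That the plan will condition on post-randomisation values, or that its estimate is biased towards no effect.** Collecting a variable at each visit does not show how it will be modelled, and the sign of any shift is unknown.
- **That MTX titration ("Then, the dose will be adjusted based on the response by 5 mg increments up to 25 mg a week") shows a covariate responding to treatment.** MTX is itself the randomised treatment, and its dose is not listed by name as a covariate.
- **That group 3 vs 4 must also use baseline values only.** Group 3 has already had more than a year of oral MTX at its baseline, so the right adjustment there depends on which effect is wanted.

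**Conclusion.** The point holds as an unresolved choice that affects the target of the only randomised comparison. The omission is certain on the text: there is no covariate time point, no exemption for group 1 vs 2, and no other section that supplies either. The consequence is conditional. It arises only if visit-level values are used, treatment changes them, and they affect the outcome or share causes with it. Its size and direction cannot be determined from the documents, and it may be negligible. The figures above show how a shift would behave under assumed inputs; they are not evidence of bias in this trial. Because an ordinary reading of the text would change the estimand without saying so, and the remedy needs no new data, the section should be amended.

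**What to change.** In the Statistical methods section, state that the primary group 1 vs group 2 contrast adjusts only for covariates measured at baseline. State also that, for this contrast, visit-level DAS28, ESR/CRP, 5-MTHF and concomitant-drug values are used only in mediation or sensitivity analyses labelled as such.

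The baseline values are already collected, so the cost is wording and a little more analysis. Some precision may be lost. In the simulation with slope 0.3 and no arm difference in the covariate, the standard error was 0.197 SD with baseline adjustment, against 0.190 and 0.184 SD with visit-level adjustment. That is 0.197/0.190 = 1.04 and 0.197/0.184 = 1.07, or about 4% to 7% larger under those assumed inputs.

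### The split of the MTX effect into direct and MTX-PG-mediated parts rests on an unstated linear extrapolation, because MTX-PGs arise only under MTX

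*Combined protocol and SAP*

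**What the plan says.** The Statistical methods section plans linear mixed models and then adds: "we will also use mediation analysis to assess the potential direct and indirect effects of MTX-PGs, adenosine concentrations and genetic polymorphisms". The same sentence describes these as effects "on the associations between MTX, BP and markers of arterial function". Inference is by bootstrap in software that "provides appropriate bootstrapping routines for estimating the non-parametric 95% CIs of indirect effects". The section does not say which groups or visits enter the MTX-PG model, on what scale PG is used, what response shape is assumed, or whether an MTX-by-PG interaction is fitted.

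The MTX-polyglutamates paragraph says that "RBCs MTX-PGs concentrations will be measured at each assessment visit with a validated LC-MS/MS assay", with no restriction to MTX-treated patients.

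The description of the four groups fixes who can have MTX-PGs:

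- Group 1 starts MTX at entry, and "the dose will be adjusted based on the response by 5 mg increments up to 25 mg a week".
- Group 2 takes sulfasalazine; use of "other DMARDs (except MTX), is allowed during the study period".
- Group 3 has taken oral MTX for over a year at baseline and switches route at an unchanged dose.
- Group 4 stays on other synthetic DMARDs.

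**The concern.** A mediation analysis asks what MTX would do if the mediator were held at a given level. Here the mediator is made from the exposure. After baseline, essentially no one in the randomised pair is off MTX with measurable MTX-PGs, and patients on MTX are expected to have them. Nothing observed directly informs the effect of MTX at zero MTX-PG, yet that quantity is what the direct effect means in this comparison.

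The PG slope must then come from differences among MTX-treated patients, and in group 1 those differences are partly produced by titrating dose on response. Randomising MTX does not protect that slope from confounding.

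What is at stake is a named mechanistic result. A flat or saturating concentration-response could be read as MTX acting other than through its polyglutamates when the whole effect runs through them. The bootstrap interval would not reveal this, because it measures sampling error around the extrapolation and does not test the extrapolation. The main treatment comparison is not affected.

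**Working it through.** **Inputs from the documents.** 31 patients per group, 1:1 randomisation of groups 1 and 2, 95% bootstrap intervals. No effect size, SD, power or PG distribution is given, so there is no figure of the plan's own to reproduce. Everything else below is assumed.

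**1. What the model estimates.** Take Y = a + c′X + bM, with X = MTX (1/0), M = MTX-PG, and M = 0 in all controls. Least squares then gives exactly:

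- b = slope of Y on M within MTX patients; controls add nothing to it;
- indirect effect = b × mean M in MTX patients;
- c′ = the MTX patients' fitted line at M = 0, minus the control mean.

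On one simulated data set of 31 v 31, the joint model and the within-MTX line gave the same b (0.742) and the same c′ (0.392). A true direct effect and a PG-driven step effect (any PG gives the full effect) produce identical data.

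**2. Size of the mislabelling.** Let the effect act wholly through PG as m/(k + m), with mean PG set to 1 and k the half-maximal level. At the mean, the slope is k/(1+k)² and the effect is 1/(1+k). The linear split therefore assigns k/(1+k) to the indirect effect and 1/(1+k) to the direct effect. The truth is 0% direct.

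| PG-response | 1/(1+k) | Simulated, lognormal PG, CV 0.4–0.6 |
|---|---|---|
| k = 0.25 | 80% | 79–81% |
| k = 0.5 | 67% | 66–69% |
| k = 1.0 | 50% | 51–54% |
| linear | 0% | about 0% |

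With gamma-distributed PG (CV 0.3–0.7) the large-sample shares are 76–79% at k = 0.25 and 50–51% at k = 1.0; a step response gives 100%. If PG is measured with reliability 0.7, even the linear case gives 1 − 0.7 = 30% direct.

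**3. Precision when the linear model is true.** Assume residual SD 8 mm Hg and a total effect of −5 mm Hg.

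- Indirect effect: SE ≈ 8/(√31 × CV), which is 8/(5.57 × 0.4) = 3.6 at CV 0.4 and 8/(5.57 × 0.6) = 2.4 at CV 0.6. Simulation, which also carries the sampling variation of PG itself, gives 2.7–4.0 mm Hg.
- Total effect: 8 × √(2/31) = 2.03. Adding the PG-driven spread of 5 × 0.5 = 2.5 mm Hg in the MTX arm gives √[(64 + 6.25)/31 + 64/31] = 2.08, about 2.1.
- Collinearity of arm and PG: R² = 1/(1 + 2CV²) = 0.76 at CV 0.4 and 0.67 at CV 0.5. The SE of the direct effect is inflated by 1/√(1 − R²) = 2.0 and 1.7.

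**4. How often the wrong label would be significant.** With 31 v 31, gamma PG with CV 0.5, a total effect of 0.72 SD wholly through PG, 600 runs and a 400-draw percentile bootstrap, a significant direct effect appeared in:

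- 5.5% of runs if linear;
- 14% at k = 1.0;
- 27% at k = 0.25;
- 36% for a step.

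In the linear case the mean split was correct (indirect 0.71 SD, direct 0.00), but the indirect effect was detected in only 51% of runs.

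**5. Group 3 in a replacement analysis.** Baseline already reflects over a year of MTX. If BP tracks PG linearly, regressing change in BP on PG level recovers only (1 − ρ) of the slope, where ρ is the within-patient PG correlation and variances are equal: 30%, 20% or 10% for assumed ρ of 0.7, 0.8 or 0.9. Group 3 therefore needs change in PG, not its level.

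**The case against.** A reader might infer that the split cannot be estimated at all. That is too strong: with a response linear through zero, no interaction, no measurement error and no confounding, it is recovered without bias (step 4). The valid complaint is that these conditions are unstated and unchecked.

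Nor do the documents commit to the model in step 1. The wording is loose and also permits MTX-PG as an exposure within MTX patients, where the structural zero does not arise. This stands as a limit on certainty. The MTX versus no-MTX split remains the most natural reading, and the silence about groups leaves it open.

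It is tempting to call MTX-PG zero in every comparator. That is firm for group 2 only. Group 4 is defined by current treatment; the exclusion criteria neither bar past MTX nor set a washout, so near-zero values there are an inference. Low PG values early in group 1 might also shorten the extrapolation, but the documents give no PG values.

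One might also infer that titration confounding is ignored. It is not: the plan adjusts for DAS28, inflammatory markers and the doses of drugs that may affect BP, and DAS28 and CRP are collected at every visit. What remains is that the timing of these covariates relative to each PG value is not set.

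Finally, a saturating effect would not always be reported as direct. In step 4 that label was significant in 14–36% of runs under saturating or step responses; in the rest the direct effect was not significant.

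**Conclusion.** The concern holds in a limited form. Read as an MTX versus no-MTX comparison, the MTX-PG split is identified only through linearity, no-interaction, no-measurement-error and no-confounding conditions that the plan neither states nor tests. Under saturation, roughly half to four-fifths of a wholly PG-driven effect would be labelled direct; under linearity, none would, but the indirect estimate would be about 1.3 to 1.9 times as variable as the total effect (2.7/2.1 to 4.0/2.1).

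These sizes rest on assumed PG variability, response shape, residual SD and effect size. The repeated-visit mixed model was not simulated. The point is specific to MTX-PGs: adenosine can be measured in all groups, so its mediation analysis is not affected. The change should be made, because the possible error is a wrong mechanistic conclusion that the planned interval cannot expose.

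**What to change.** In Statistical methods, take MTX-PGs out of the between-group mediation analysis and analyse them as exposure-response within MTX-treated patients (groups 1 and 3):

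- Use the planned mixed models and covariates, with DAS28 and inflammatory markers measured before each PG value and not only at baseline, since group 1 dose follows later response.
- Group 1: relate change in BP, AIx and PWV from the pre-MTX baseline to on-treatment MTX-PG.
- Group 3: relate change in outcome to change in MTX-PG, or separate within-patient from between-patient PG effects.
- Show the two groups separately, report slopes with CIs, describe them as observational, and make no direct/indirect claim for MTX-PGs.
- Use MTX-PG values in groups 2 and 4 only to confirm non-exposure.

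Samples, assays and visits are unchanged. The cost is the loss of a statement on the percentage of the effect mediated by MTX-PGs.

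### Genotype is analysed through mediation and indirect effects, with no treatment-by-genotype term, so the planned output does not estimate how the MTX effect differs by genotype

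*Combined protocol and SAP*

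**What the plan says.** The Statistical methods section sets out linear mixed models for the treatment effects and then a "mediation analysis to assess the potential direct and indirect effects of MTX-PGs, adenosine concentrations and genetic polymorphisms on the associations between MTX" and the vascular outcomes. The software is chosen because it offers "bootstrapping routines for estimating the non-parametric 95% CIs of indirect effects". Genotype thus stands in the same list as two biomarkers measured after treatment starts. The section does not say whether a polymorphism is exposure, mediator or moderator, or which groups and visits enter the model. Its list of adjustment variables contains neither genotype nor any interaction.

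The paragraph on genetic polymorphisms lists 13 SNPs, chosen because they were "shown to be important in the effect of MTX in RA, or demonstrating a theoretical association with the cardiovascular effects of MTX". It adds one more locus: "In addition, the number of 28 base-pair repeats in the promoter region of thymidylate synthase will be determined by PCR". That makes 14.

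On design, the study population paragraph says that "Demographic and clinical characteristics and genetic polymorphisms will be assessed at baseline", and that groups 1 and 2 "will be randomized to either subcutaneous MTX (group 1) or sulfasalazine (group 2, age- and sex-matched) in a 1:1 ratio". In group 2, use of "other DMARDs (except MTX), is allowed during the study period". Groups 1 and 3 take MTX; groups 2 and 4 do not. Each has 31 patients.

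**The concern.** The reason given for choosing the loci is their part in the effect of MTX. That is a question of effect modification: does the MTX effect on BP differ between genotypes? The stated output is an indirect effect, which is a different quantity. Genotype is fixed before treatment, so treatment cannot act through it.

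An analyst who follows the text could fit genotype in two ways, and neither answers the question. As a mediator in the randomised comparison, it would give an estimate near zero however strong the pharmacogenetics, and that could be reported as no genetic contribution. As an upstream cause acting through MTX-PGs, it would give a diluted estimate if patients without MTX are in the same model, because the path does not exist in them.

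**Working it through.** The plan gives no figure for this analysis: no SD, allele frequency, effect size or power. The group sizes (31 each), the 1:1 randomisation, the visits and the bar on MTX in group 2 come from the document. All other inputs below are assumed.

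**1. Genotype as mediator, groups 1 vs 2.** The indirect effect is a × b, where a is the treatment effect on allele count and b is the genotype slope on the outcome given treatment. Randomisation makes a zero in expectation. In one trial a differs from zero only by chance, with SE = sqrt(2 × 2p(1-p)/31):
- p = 0.1: sqrt(2 × 0.18/31) = 0.11 alleles
- p = 0.3: sqrt(2 × 0.42/31) = 0.16
- p = 0.5: sqrt(2 × 0.50/31) = 0.18

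Simulation with 5,000 trials per frequency, outcome SD 10 mmHg, genotype main effect 2 and treatment-by-genotype effect 4 mmHg per allele:

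| Allele frequency | Mean indirect effect | Mean interaction estimate |
|---|---|---|
| 0.1 | 0.05 | 3.9 |
| 0.3 | 0.04 | 4.0 |
| 0.5 | -0.01 | 4.0 |

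The small positive means reflect slight finite-sample correlation between the estimates of a and b. At p = 0.3 the bootstrap 95% interval for the indirect effect excluded zero in 2.3% of 600 trials, although the modification was real.

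**2. Genotype as a cause acting through MTX-PGs.** MTX-PG is taken as zero in records without MTX. If MTX and non-MTX records are pooled with no interaction, the genotype-to-MTX-PG slope is the slope in MTX users times the share of records on MTX. The indirect effect shrinks by the same share if treatment is in the outcome model.
- After baseline, equal groups: 62/124 = 0.50. Simulated ratio 0.49 to 0.51.
- All four groups with baseline records: group 1 gives 2 MTX records per patient and group 3 gives 3, so (2 + 3)/12 = 0.42. Simulated 0.42.
- Groups 1 and 2 with baseline records: 2/6 = 0.33. Simulated 0.33.
- Group 1 alone at 6 months: simulated 1.00.

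If treatment is left out of the outcome model and MTX also acts by another route (assumed -5 or +5 mmHg, with MTX-PG slope 0.1, mean 60 plus 10 per allele, SD 25), the post-baseline ratio is about 0.2 or 0.8.

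**3. What the interaction test can detect.** With change SD 10 mmHg, SE = 10 × sqrt(2/(31 × 2p(1-p))):
- p = 0.1: 10 × sqrt(2/5.58) = 6.0
- p = 0.4: 10 × sqrt(2/14.88) = 3.7

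Multiplied by 2.80 (80% power, two-sided 5%), this gives about 10 to 17 mmHg per allele at one locus. Multiplied by 3.76 (level 0.05/14), it gives about 14 to 23.

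**The case against.** The strongest reply is that the plan speaks of effects on associations, which is ordinary language for moderation, and that the SNPs were chosen with that in mind. The section writes out no model terms at all, so a missing interaction may be brevity rather than a decision. This stands in part: a reader might infer that the plan has settled on genotype as a mediator, and the text does not support that. But the only analysis named is mediation and the only output named is an indirect effect, and neither delivers moderation.

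A reader might also infer that the genotype path will be halved. The documents do not say that MTX and non-MTX groups are pooled for this path, nor how treatment is coded. One half is a conditional figure; other choices give 0.33, 0.42, or about 0.2 or 0.8.

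A reader might further infer a spurious indirect effect in groups 3 and 4, which are not randomised. Selection by genotype is possible there, but the documents give nothing from which to size it. On a change outcome, a genotype effect on BP level alone would cancel.

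Finally, an indirect effect of zero through genotype is a correct answer to its own question. The harm comes only when it is read as a test of pharmacogenetic difference. Given why the loci were chosen, that reading is likely.

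**Conclusion.** The point holds as a mismatch between question and method. The named analysis does not estimate how the MTX effect varies with genotype. Fitted as a mediator in groups 1 and 2, genotype has an indirect effect of zero in expectation; this follows from randomisation and needs no assumed SD. Fitted as a cause acting through MTX-PGs with MTX and non-MTX groups pooled and no interaction, the effect is diluted to about half after baseline, and further if baseline records are included. That second result rests on pooling, on MTX-PG being zero without MTX, and on treatment being in the model. The main mixed-model treatment effects are unaffected and the genetic analyses are best regarded as exploratory, so the point is minor.

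**What to change.** Do not report indirect effects through genotype. State instead:

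1. **Moderation.** In the mixed model for groups 1 and 2, test each of the 14 loci through treatment × genotype × visit with all lower-order terms. Use allele count for the SNPs and repeat count for thymidylate synthase. Report the 6-month treatment-by-genotype contrast.
2. **Paths through MTX-PGs.** Fit these only in MTX-treated records: groups 1 and 3 with a group term for genotype on MTX-PG level, and group 1 after baseline for any genotype-to-MTX-PG-to-BP path. Group 3 is left out of the BP path because its baseline BP already follows more than a year of MTX. Show results with and without adjustment for MTX dose, because in group 1 "the dose will be adjusted based on the response by 5 mg increments up to 25 mg a week" and dose changes could mask a genotype effect on MTX-PG level.
3. **Reporting.** Give all 14 estimates and confidence intervals as exploratory, with false-discovery-rate control over the loci in each set.

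The cost is SAP wording and model code; no new data are needed. The drawback is low power. Under the assumptions above, one locus needs about 10 to 17 mmHg per allele for 80% power. For genotype on MTX-PG level in 62 MTX users, a locus must explain about 12% of the variance (Fisher z: tanh(2.80/sqrt(59)) = 0.35, squared 0.12). The gain is therefore an estimate and interval for the right quantity, not a realistic chance of detecting modest effects.
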